1.0 Introduction

This document presents the statistical analysis plan (SAP) for the Anika Therapeutics, Inc. protocols CINGAL 20-01 (Hip), CINGAL 20-02 (Shoulder), and CINGAL 20-03 (Ankle). This SAP incorporates the data listings, summary tables, and statistical analyses. This document is based on the original final protocols and case report forms (CRFs) for each study.

The three studies are the same except for the anatomical area of interest and so all of the analyses will be consolidated into a single SAP.

2.0 Study Design

This is a prospective, expanded indications multi-center, open-label study to evaluate safety and performance of injection of Cingal for relief of pain in patients with a diagnosis of an osteoarthritic hip joint (CINGAL 20-01), shoulder joint (CINGAL 20-02), and ankle joint (CINGAL 20-03).

The subjects in each of these studies will be patients with a diagnosis of osteoarthritic (OA) joint who the investigator determines are appropriate candidates for treatment with an injection of CINGAL.

In each study, up to 25 subjects will be enrolled and treated at up to 10 investigational sites in the EU. Subject participation will last approximately 6 Months, with visits scheduled at Screening, Baseline, 1 month, 3 month and 6 months.

3.0 Objectives

The goal of these studies is to demonstrate the clinical improvement and safety in patients treated with CINGAL for hip osteoarthritis, shoulder osteoarthritis, and ankle osteoarthritis. Specifically, this study will provide confirmation to the effectiveness and safety of CINGAL at relieving the specified joint pain to 6 months post-treatment.

PRIMARY ENDPOINT:

• Reduction of index joint Numerical Rating Scale (NRS) pain on walking from baseline to 6 Months post injection (CINGAL 20-01), joint pain from baseline to 6 Months post injection (CINGAL 20-02), and pain on walking from baseline to 6 Months post injection (CINGAL 20-01).

SECONDARY ENDPOINTS:

- Improvement in Lequesne Hip index joint from baseline to 6 months post injection. (CINGAL 20-01 only)
- Improvement in DASH score for index joint from baseline to 6 months post injection (CINGAL 20-02 only)

- Improvement in AOFAS index joint from baseline to 6 months post injection (CINGAL 20-03 only).
- Improvement in Patient Global Assessment (PGA) from baseline to 6 months post injection.
- OMERACT-OARSI responder rate in the index joint at 6 months post injection.
- Time to treatment failure
- Reduction in Medication usage from baseline to 6 months post injection.

EXPLORATORY ENDPOINTS

Any comparisons across timepoints (baseline to 6 months) not described in the primary or secondary endpoints, including but not limited to:

- Demographics
- Medical History
- History of joint osteoarthritis
- Rescue Medication Use
- Treatment Failure
- Injection procedure
- Concomitant medications
- Non-drug therapy

SAFETY ENDPOINT:

The incidence, severity, and relationship to treatment of all Adverse Events (AE) will be collected from the treatment injection to the 6 month assessment.

4.0 Statistical Methods in Protocol

4.1 STATISTICAL METHODS

This Statistical Analysis Plan provides the details of the statistical analysis of the study data that is described in the protocol.

4.1.1Sample Size

The primary analysis will be the mean change in index joint pain from baseline to 6 months as measured by the Numerical Rating Scale.

The hypothesis to be tested is:

H₀: $\mu_{DMON} = 0$ versus H_A: $\mu_{DMON} > 0$.

In this hypothesis, μ_{DMON} is the mean change in pain on walking from baseline at 6 Months in CINGAL treated patients.

The data will be analyzed via a one sample t-test.

It is assumed that a mean change in pain from baseline of 2 points represents a clinically significant improvement with a standard deviation of 2 - 2.5 points, for 80% power and alpha of 5% then a total of 15 subjects are required. To ensure sufficient subjects are available at the 6 month follow up, it is proposed to enroll and treat at least 25 subjects which should be more than adequate to demonstrate that treatment of the study population with CINGAL would reduce joint pain at 6 months.

Single sites should not enroll more than 75% of the total enrollment.

4.1.2 Primary Efficacy Endpoint

4.1.2.1 The mean change in index joint Pain from baseline to 6 Months as measured with NRS comparing the CINGAL treated group to baseline measurements .

The primary analysis will be the mean change in index joint pain from baseline to 6 months as measured by the Numerical Rating Scale.

The hypothesis to be tested is:

H₀: $\mu_{DMON} = 0$ versus H_A: $\mu_{DMON} > 0$.

In this hypothesis, μ_{DMON} is the mean change in pain on walking from baseline at 6 Months in CINGAL treated patients.

The data will be analyzed via a one sample t-test.

This will be analyzed using SAS PROC UNIVARIATE. ODS statements will be used to output the descriptive statistics and p-values into data sets that can be easily displayed using PROC REPORT.

The tables for this analysis will be displayed as follows showing all time points for reference:

This analysis will be performed for each of the protocols

Summary of Differences in Mean Responses over time -

Time Perios			Visit Result	
	Descriptive Statistic	Baseline Result		Change from Baseline
1 Week	N			
	Mean			
	Std.Drv			
	Median			
	(Min,Max)			
	p-value diff=0			
1 Month	N			
	Mean			
	Std.Drv			
	Median			
	(Min,Max)			
	p-value diff=0			
•••				
6 Months	Ν			
	Mean			
	Std.Drv			
	Median			
	(Min,Max)			
	p-value diff=0			

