9.2.3 Subject Populations

The Safety Population will be defined as all subjects who undergo Study Treatment, and the safety analysis will be performed on this population.

The primary analysis on the primary endpoint will be performed on the Intent to Treat (ITT) population, defined as all patients who were treated in the study. All Primary and Secondary endpoints will be analyzed using the ITT population.

A secondary analysis will be conducted on the Per Protocol (PP) population. Since the primary endpoint is at 6 Months, this is all subjects who complete the 6 Month assessment and who do not have a major deviation from the protocol. For all other assessments, this is defined as the subjects who complete those assessments according to the protocol.

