This will be analyzed for each of the protocols and tabled like the primary endpoint in section 4.1.2.1.

4.1.3.4 Responder index based on OMERACT- OARSI responder index at 1 Month, 3 Months and 6 Months.

The response rate for each time point will be tabulated and exact 95% confidence intervals will be calculated.

This will be estimated and tested using PROC FREQ with the BINOMIAL option. The results will be displayed similar to:

Summary of the OMERACT-OARSI Responder Rates at each visit and each protocol.

Parameter	1 Week	1 Month	3 Months	6 Months
Estimate n/N (%)				
95% Confidence Interval				

4.1.3.5 Time to Treatment Failure.

The time to treatment failure will be assessed via the estimation of the Kaplan-Meier curve. This will be done via the PROC LIFEREG procedure in SAS. The estimate of the median survival time and the 95% confidence intervals will be reported. This will be done for each protocol.

For all studies, a patient is considered a treatment failure if any of the following occur:

Corticosteroid injections Shock-wave therapy Dry Needling Nitroglycerin patches Prolotherapy (PrT). Platelet / PRP / BMAC injection Hyaluronic Acid. Surgical treatment – open or arthroscopic

4.1.3.6 Reduction in Pain Medication usage at 1 Month, 3 Months and 6 Months.

The reduction from baseline in the mean reduction of medication usage at each time point will be tabulated and 95% confidence intervals will be calculated.

This will be estimated using PROC MEANS. The results will tabled like the primary endpoint in section 4.1.2.1.

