4.5 SUBJECT POPULATIONS

All safety analyses will be conducted on all subjects who undergo treatment in any group.

The Safety Population will be defined as all subjects who undergo at least one Study Treatment, and the safety analysis will be performed on this population.

The primary analysis on the primary endpoint will be performed on the Intent to Treat (ITT) population, defined as all patients who were treated in the study. All Primary and Secondary endpoints will be analyzed using the ITT population.

A secondary analysis will be conducted on the Per Protocol (PP) population. Since the primary endpoint is at 6 Months, this is all subjects who complete the 6 Month visit and who do not have a major deviation from the protocol. For all other assessments, this is defined as the subjects who complete those assessments according to the protocol.

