4.6 ADDITIONAL ANALYSES

All of the analyses are performed on the data with the specified covariates or other factors assumed in the model. If it is determined that certain factors may influence the outcomes of the endpoints, then additional analyses will be performed

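### The primary analysis is assigned to all treated patients, but the planned t-test can use only those with a 6-month NRS and no missing-score rule is stated; if poor responders leave, the mean reduction is overstated

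*SAP*

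**What the plan says.** - **Population.** SAP 4.5 makes the Intent to Treat set primary, "defined as all patients who were treated in the study". Protocol 9.2.3 has the same definition and adds: "All Primary and Secondary endpoints will be analyzed using the ITT population".
- **Method.** SAP 4.1.2.1 gives one method for the 6-month change in NRS: "The data will be analyzed via a one sample t-test", in PROC UNIVARIATE. The table shell shows N, mean, SD and a p-value visit by visit. Earlier visits do not enter the 6-month estimate.
- **Secondary set.** For Per Protocol, SAP 4.5 says "this is all subjects who complete the 6 Month visit and who do not have a major deviation from the protocol".
- **Allowance for loss.** SAP 4.1.1 states "for 80% power and alpha of 5% then a total of 15 subjects are required", and then: "To ensure sufficient subjects are available at the 6 month follow up, it is proposed to enroll and treat at least 25 subjects". No dropout rate is given.
- **Missing scores.** Neither document has an imputation rule, a model that uses the interim scores, or a missing-data sensitivity analysis. The baseline rule (last pre-treatment value) concerns baseline only. The protocol's reference list includes a report on missing data, but the text does not cite it. SAP 4.6 offers only this: "If it is determined that certain factors may influence the outcomes of the endpoints, then additional analyses will be performed".
- **Data available.** Protocol 7.1 schedules the NRS at baseline and at 1, 3 and 6 months.

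**The concern.** A treated subject with no 6-month NRS has no 6-month change, so the t-test leaves that subject out. The result labelled ITT is then a result in subjects seen at 6 months. The Per Protocol analysis cannot act as a check, because it makes the same restriction and then removes major deviations as well.

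Treating 25 where 15 are needed protects power. It does not protect the estimate if those who leave differ from those who stay. There is no control arm in which similar losses might partly cancel, so the 6-month mean reduction is the main efficacy finding, and selective loss of poor responders would inflate it directly. With about 25 subjects, a missing-data method chosen after the scores are seen would be open to challenge.

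**Working it through.** **1. The plan's own figure.** Inputs from SAP 4.1.1: mean change 2, SD 2 to 2.5, power 80%, alpha 5%. An exact one-sample t-test, two-sided, with SD 2.5 needs n = 15 (noncentrality 2/2.5 × √15 = 3.10, power 82.1%). At SD 2, 15 subjects give 94.9%. The stated 15 reproduces. The margin is 25 − 15 = 10 subjects, or 40% of those treated.

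**2. Simple arithmetic.** If k of 25 are missing, the completer mean exceeds the all-treated mean by (k/25) × (completer mean − mean among the missing). Suppose completers average 2.0:
- 5 missing who average 0: 5/25 × 2 = 0.40. If they average 1: 0.20.
- 10 missing who average 0: 10/25 × 2 = 0.80. If they average 1: 0.40.
- Missing subjects who also average 2.0: 0.

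**3. Graded selection.** The assumptions below are not in the documents, except mean 2 and SD 2.5 (the upper SD in SAP 4.1.1). Let z be the standardised reduction that drives loss (higher is better), with P(loss) = 1/(1 + exp(−(a − z))). The odds of loss then rise by a factor e per SD of worse score, and a is set to give the overall loss. Integrating over a standard normal z gives the mean z among those retained: d = 0.173 at 20% loss (a = −1.65) and d = 0.332 at 40% loss (a = −0.49). Bias = r × 2.5 × d, where r is the correlation between the score driving loss and the 6-month score, and r = 1 if loss depends on the 6-month score itself.

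| Loss | 3-month score drives loss, r = 0.3 / 0.5 / 0.7 | 6-month score drives loss | 95% CI coverage (6-month case) |
|---|---|---|---|
| 20% | 0.13 / 0.22 / 0.30 | 0.43 | about 88% |
| 40% | 0.25 / 0.41 / 0.58 | 0.83 | about 75% |

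Coverage is from simulation with 25 treated. (The formula gives 0.415 for the middle 40% entry; simulation gives 0.41.) If loss is completely random, the bias is 0.

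**4. Sensitivity to the mechanism.** Drawing exactly 5 or 10 of 25 to be lost, with weights exp(−z) on the 6-month score, is a somewhat stronger selection. It gives bias of about 0.47 and 0.97, with coverage about 85% and 62%. In those runs, including random and 3-month-driven loss, the test against zero succeeded in 82% of trials or more. With 20% lost by the same weights, the bias stays at about 0.47 to 0.49 for 25, 100 or 250 subjects, so more enrolment does not remove it.

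**5. What a repeated-measures model recovers.** This was fitted to 1-, 3- and 6-month changes with 5 of 25 lost by the weights in step 4, all leaving after the 3-month visit, using Satterthwaite degrees of freedom (855 to 994 fitted trials per setting). Bias is 0.02 or less in size when loss is random or driven by the 3-month score (coverage 93 to 95%). When the unseen 6-month score drives loss, 0.40 / 0.32 / 0.22 remains at r = 0.3 / 0.5 / 0.7, against about 0.47 for completers.

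**6. Missing set to baseline.** With 5 of 25 missing completely at random and a true mean of 2, the bias is −5/25 × 2 = −0.40. The mean CI width is 1.95, against 2.31 for completers, because imputed constants count as observations.

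**The case against.** **Informative loss is assumed, not shown.** Treatment is a single injection, so there is no later dosing to stop. Lack of efficacy is not among the example withdrawal reasons in protocol 13.12, although subject request and the open category could cover it. Treatment failure is not said to end follow-up, and protocol 13.4 keeps subjects with deviations in follow-up. This stands, and it is why the point is conditional.

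**There are safeguards.** N is printed for each visit, three contact attempts are required (protocol 7.5), and withdrawn subjects are asked back. The request names safety evaluations, but the NRS is taken at the same visits, so a returning subject could supply one. The Kaplan-Meier analysis of treatment failure includes early leavers until censoring. These measures may limit loss or make it visible. None of them corrects the 6-month mean.

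**The remedies are imperfect.** Step 5 is a favourable case, since every leaver supplied a 3-month score. Baseline imputation under random loss errs by about as much as the bias it guards against. Both limits stand and should be stated with the results.

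**Scores after other treatment.** SAP 4.1.3.5 lists events under "For all studies, a patient is considered a treatment failure if any of the following occur". A reader might infer that 6-month scores after such events are wrongly included. The documents do not support that: using observed scores regardless is a legitimate reading. A sensitivity analysis for these scores is optional and not part of this point.

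**Conclusion.** The mismatch is real. The primary set is all treated patients, the stated method reaches only those with a 6-month NRS, and no rule connects the two. The consequence is conditional: the mean reduction is overstated if poor responders leave more often, unbiased if loss is unrelated to response, and understated if good responders leave. Because no dropout rate is given, the figures in step 3 illustrate a range and do not estimate this trial's bias.

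Three stronger readings are tempting and not supported:
- *The plan expects 40% loss.* It does not. That is the full margin between 25 and 15, not a stated assumption.
- *The trial is underpowered or its test would fail.* The 15 reproduces, and at a true mean of 2 the test usually still succeeds. What is mainly at risk is the reported size of the reduction and its interval.
- *Overstatement could carry the result past a 2-point success threshold.* SAP 4.1.1 uses 2 points for sample size; the test is against zero.

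This should be fixed before analysis, but it does not undermine the design.

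**What to change.** In SAP 4.1.2.1:

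1. Beside the t-test, estimate the 6-month mean change with a 95% CI from the 1-, 3- and 6-month changes in a repeated-measures mixed model: visit, centred baseline NRS, unstructured covariance, Kenward-Roger degrees of freedom, and a stated fallback if it does not converge. Fix before analysis which of the two estimates is primary.
2. Add one sensitivity analysis in all treated subjects that sets missing 6-month scores to baseline. State that it can understate the effect (about −0.4 points with 5 of 25 missing completely at random and a true mean of 2), is not a worst case, and has too narrow a CI.
3. Report the number of subjects with a missing 6-month score next to the primary result.

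State the limits of the model: it reduces bias when loss depends on observed scores, leaves part of it when loss depends on the unseen 6-month score, and gains less for subjects who leave before the 3-month visit. Those with no post-baseline score are covered only by item 2.

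The cost is SAP wording and a little programming. No new visits, data or patients are needed, since the NRS is already collected. The downside is that the report will carry several estimates that can differ, and the headline figure may be less favourable.

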4.1.3 Secondary Efficacy Endpoints

4.1.3.1 Improvement in Lequesne Hip index joint from baseline to 6 months post injection. (CINGAL 20-01 only)

Since this is a secondary endpoint the data will be analyzed for each time point individually with no adjustments for multiplicity Data will be analyzed via a one sample t-test on the difference between the month elbow pain score and the baseline elbow pain score. Formally, the hypothesis to be tested is:

H₀: μ _{DMON} = 0 versus H_A: μ _{DMON} >0.

In this hypothesis, μ_{DMON} is the mean change from baseline at a time point for CINGAL treated patients.

This will be analyzed using SAS PROC UNIVARIATE. ODS statements will be used to output the descriptive statistics and p-values into data sets that can be easily displayed using PROC REPORT.

This will be analyzed and tabled like the primary endpoint in section 4.1.2.1.

4.1.3.2 Improvement in AOFAS index joint from baseline to 6 months post injection (CINGAL 20-03 only).

Since this is a secondary endpoint the data will be analyzed for each time point individually with no adjustments for multiplicity Data will be analyzed via a one sample t-test on the difference between the month elbow pain score and the baseline elbow pain score. Formally, the hypothesis to be tested is:

H₀: μ _{DMON} = 0 versus H_A: μ _{DMON} >0.

In this hypothesis, μ_{DMON} is the mean change from baseline at the time points for CINGAL treated patients.

This will be analyzed using SAS PROC UNIVARIATE. ODS statements will be used to output the descriptive statistics and p-values into data sets that can be easily displayed using PROC REPORT.

This will be analyzed and tabled like the primary endpoint in section 4.1.2.1.

4.1.3.3 The mean and percent change in Patient Global Assessment from Baseline to 1 Months, 3 Months and 6 Months.

Since this is a secondary endpoint the data will be analyzed for each time point individually with no adjustments for multiplicity Data will be analyzed via a one sample t-test on the difference

between the month elbow pain score and the baseline elbow pain score. Formally, the hypothesis to be tested is:

H₀: $\mu_{DMON} = 0$ versus H_A: $\mu_{DMON} > 0$.

In this hypothesis, μ_{DMON} is the mean change from baseline the time points for CINGAL treated patients.

This will be analyzed using SAS PROC UNIVARIATE. ODS statements will be used to output the descriptive statistics and p-values into data sets that can be easily displayed using PROC REPORT.

This will be analyzed for each of the protocols and tabled like the primary endpoint in section 4.1.2.1.

4.1.3.4 Responder index based on OMERACT- OARSI responder index at 1 Month, 3 Months and 6 Months.

The response rate for each time point will be tabulated and exact 95% confidence intervals will be calculated.

This will be estimated and tested using PROC FREQ with the BINOMIAL option. The results will be displayed similar to:

Summary of the OMERACT-OARSI Responder Rates at each visit and each protocol.

Parameter	1 Week	1 Month	3 Months	6 Months
Estimate n/N (%)				
95% Confidence Interval				

4.1.3.5 Time to Treatment Failure.

The time to treatment failure will be assessed via the estimation of the Kaplan-Meier curve. This will be done via the PROC LIFEREG procedure in SAS. The estimate of the median survival time and the 95% confidence intervals will be reported. This will be done for each protocol.

For all studies, a patient is considered a treatment failure if any of the following occur:

Corticosteroid injections Shock-wave therapy Dry Needling Nitroglycerin patches Prolotherapy (PrT). Platelet / PRP / BMAC injection Hyaluronic Acid. Surgical treatment – open or arthroscopic

4.1.3.6 Reduction in Pain Medication usage at 1 Month, 3 Months and 6 Months.

The reduction from baseline in the mean reduction of medication usage at each time point will be tabulated and 95% confidence intervals will be calculated.

This will be estimated using PROC MEANS. The results will tabled like the primary endpoint in section 4.1.2.1.

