6. ENDPOINTS

6.1 Primary Endpoint:

 Reduction of index ankle Numerical Rating Scale (NRS) pain on walking from baseline to 6 Months post injection.

6.2 Secondary Endpoints:

- Improvement in AOFAS index ankle from baseline to 6 months post injection.
- Improvement in Patient Global Assessment (PGA) from baseline to 6 months post injection.
- OMERACT-OARSI in the index ankle responder rate at 6 months post injection.
- Time to treatment failure
- Reduction in Medication usage from baseline to 6 months post injection.

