7. STUDY PROCEDURES

7.1 Schedule of Events

Assessments	Screening Visit	Baseline Visit	Month 1 Visit	Month 3 Visit	Month 6 Visit
Assessments	Day -14 to -7 ±2 days	Day 0	±3 days	± 7 days	± 7 days
Informed Consent	Х				
Evaluation of Enrollment Criteria	х	х			
Demographics	Х				
Vital Signs	Х				
History Joint OA (Index & Contralateral for hip, knee and ankle)	х				
Medical History	Х				
Concomitant Medication	х	Х	X	Х	х
Assess non-drug therapies	Х	Х	X	Х	х
Adverse Event Assessment		Х	X	Х	х
Collect & Review Subject Diary		Х	Х	Х	х
Rescue Medication usage / washout		Х	Х	Х	х
Patient Global Assessment (PGA)	х	Х	Х	Х	х
AOFAS index for index and contralateral ankle	х	х	Х	х	Х
Index and Contralateral Joints Pain (0-10 Numeric Rating Scale) for Hip, Knee and Ankle joints	х	х	Х	х	х
Physical Evaluation of Index and Contralateral Joints for Hip, Knee and Ankle joints	х	х	Х	х	х
Study Injection		Х			
Dispense Subject Diary	x	х	X	X	

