Appendix 1 Patient Global Assessment

To be assessed by the Subject as the first questionnaire.

The pain the subject felt in INDEX ankle caused by osteoarthritis during the last 24 hours.

Have the Subject record their response with an "X":

Think about the pain you felt in your STUDY ankle caused by your osteoarthritis during the last 24 hours.

"Considering all the ways the osteoarthritis in your STUDY ankle affects you, what is your assessment of how much your STUDY ankle is bothering you today?"

0	1	2	3	4	5	6	7	8	9	10
No Pain		Mild			Moderate	,		Severe	1	Worst Pain

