Appendix 3 American Orthopedic Foot and Ankle Score AOFAS Ankle-Hindfoot Scale (100points Total)

I Pain (40 points)

None	40
Mild, occasional	30
Moderate, daily	20
Severe, almost always present	0

II Function (50 points)

ctivity limitations, support requirement	
No limitations, no support	10
No limitation of daily activities, limitation of recreational activities, no support	7
Limited daily and recreational activities, cane	4
Severe limitation of daily and recreational activities, walker, crutches, wheelchair, brace	0

faximum walking distance, blocks	
Greater than 6	5
4-6	4
1-3	2
Less than 1	0

Walking surfaces	
No difficulty on any surface	5
Some difficulty on uneven terrain, stairs, inclines, ladders	3
Severe difficulty on uneven terrain, tairs, inclines, ladders	0

Gait abnormality	
None, slight	
Obvious	4
Markeo	0

Sagittal motion (flexion plus extension)	
Normal or mild restriction (30° or more)	8
Moderate restriction (15°-29°)	4
Severe restriction (less than 150)	0

Hindfoot motion (inversion plus eversion)	
Normal or mild restriction (75%-100% normal)	6
Moderate restriction (25%-74% normal)	3
Marked restriction (less than 25% normal)	O

Ankle-hindfoot stability (anteroposterior, varus-valgus)	
Stable	8
Definitely unstable	0

II Alignment (10 points)

Good, plantigrade foot, midfoot well aligned	15
Fair, plantigrade foot, some degree of midfoot malalignment observed, no symptoms	8
Poor, nonplantigrade foot, severe malalignment , symptoms	0

Total=100

American Orthopaedic Foot and Ankle Society

From: http://www.aofas.org/i4a/pages/index.cfm?pageid=3494

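### SAP 4.1.3.1 to 4.1.3.3 test an elbow pain score, the sign of change is undefined for scales that improve in opposite directions, and the sidedness of the primary test is left open

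*SAP*

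**What the plan says.** **Secondary tests.** SAP 4.1.3.2 is headed "Improvement in AOFAS index joint from baseline to 6 months post injection (CINGAL 20-03 only" and 4.1.3.3 is headed "The mean and percent change in Patient Global Assessment from Baseline to 1 Months, 3 Months and 6 Months". Under both headings the test is a "one sample t-test on the difference between the month elbow pain score and the baseline elbow pain score", with null mean change 0 and alternative mean change > 0. SAP 4.1.3.1 (Lequesne hip index) carries the same sentence. SAP 1.0 covers hip, shoulder and ankle studies only. For the ankle study, Protocol 7.1 schedules the "AOFAS index for index and contralateral ankle", the PGA, and NRS pain for hip, knee and ankle.

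**Scale directions.** In Protocol Appendix 3 the AOFAS pain item gives 40 points for no pain and 0 for "Severe, almost always present", so higher is better. The PGA in Protocol Appendix 1 asks "what is your assessment of how much your STUDY ankle is bothering you today" on a scale from 0 (no pain) to 10 (worst pain), so lower is better. Protocol 6.2 words the PGA endpoint as "Improvement in Patient Global Assessment (PGA) from baseline to 6 months post injection".

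**Primary test.** The endpoint in Protocol 6.1 is "Reduction of index ankle Numerical Rating Scale (NRS) pain on walking from baseline to 6 Months post injection". Protocol 9.1 and SAP 4.1.1 and 4.1.2.1 give a one-sample t-test with alternative mean change > 0. Protocol 9.1 and SAP 4.1.1 take 2 points as the effect, SD 2 to 2.5, 80% power and alpha 5%, and conclude that 15 subjects are required, with at least 25 to be treated. Neither document says whether the 5% is one-sided or two-sided. The p-value row in the SAP 4.1.2.1 table names only the null of zero difference.

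**The concern.** An analysis rule should be executable as written, and three gaps prevent that here.

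- **Variable.** The sentence defining the AOFAS and PGA tests names a measurement that the ankle study does not collect.
- **Direction.** Read literally as month minus baseline, mean change > 0 is benefit for AOFAS but worsening for PGA. It is also worsening for the primary NRS if that order is applied there. Reversing the order moves the problem to AOFAS.
- **Sidedness.** The primary hypothesis is one-sided, but the required N is the one a two-sided test gives.

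The third gap bears on the primary claim. In a single-arm, open-label study, a result between the one-sided and two-sided thresholds could be reported as success or failure depending on a choice made after the data are seen.

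**Working it through.** **Inputs** (Protocol 9.1, SAP 4.1.1): effect 2 points, SD 2 to 2.5, power 80%, alpha 5%, stated N = 15, planned enrolment 25.

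**1. Reproducing N = 15.** Exact one-sample t power is P(T > t_crit), with T noncentral t on n − 1 degrees of freedom and noncentrality (2/SD)·√n. The two-sided test adds the lower tail. Smallest n with at least 80% power:

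| Test at 5% | SD 2 | SD 2.5 |
|---|---|---|
| Two-sided | 10 (80.3%) | 15 (82.1%; n = 14 gives 79.0%) |
| One-sided | 8 (81.5%) | 12 (82.9%; n = 11 gives 79.5%) |

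The stated 15 is the two-sided result at SD 2.5. No one-sided 5% calculation in the stated SD range gives it. With n = 15 and SD 2.5, the one-sided test has 90.3% power, so 15 is still enough.

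**2. Success threshold.** Smallest significant mean improvement = t quantile × SD/√n.

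- n = 25, SD 2.5: SD/√n = 0.5. One-sided 1.711 × 0.5 = 0.86; two-sided 2.064 × 0.5 = 1.03.
- n = 25, SD 2: SD/√n = 0.4. One-sided 0.68; two-sided 0.83.
- n = 15, SD 2.5: one-sided 1.14; two-sided 1.38.

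Example at n = 25, SD 2.5: an observed mean improvement of 0.95 gives t = 0.95/0.5 = 1.90, so p = 0.035 one-sided and 0.070 two-sided.

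**3. How often the verdict changes.** This is the probability that t falls between its 95% and 97.5% quantiles.

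| True mean improvement | n = 25, SD 2.5 | n = 25, SD 2 |
|---|---|---|
| 2 points (plan) | 98.7% − 97.0% = about 1.8% | 99.9% − 99.8% = about 0.16% |
| 1 point (assumed here, half of plan) | 13.3% | 11.4% |
| 0 | 2.5% | 2.5% |

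The 1.8% and 0.16% come from unrounded powers (0.9874 − 0.9696 and 0.9993 − 0.9977). If only 15 complete at SD 2.5 and the true effect is 2 points, the figure is 90.3% − 82.1% = 8.2%. At zero effect, the chance of claiming benefit is 5% one-sided and 2.5% two-sided.

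**4. Direction.**

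| Order of subtraction | AOFAS: > 0 means | PGA and NRS: > 0 means |
|---|---|---|
| Month − baseline | improvement | worsening |
| Baseline − month | worsening | improvement |

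No single order makes the alternative mean benefit on both secondary scales. The documents give no effect size or SD for PGA. Borrowing the NRS inputs as an illustration (true change −2, SD 2.5, n = 15), a one-sided test of > 0 on month minus baseline has power of about 0.000002.

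**The case against.** **Is the endpoint itself in doubt?** A reader might infer so from the elbow wording. It is not: the section headings and both endpoint lists name AOFAS and PGA. This is carried-over text, though it sits in the sentence that defines the test.

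**Would a PGA benefit be missed?** A reader might infer this from the literal month-minus-baseline reading. The documents do not support it. A difference between two scores fixes no order, each section defines its own mean change, and both endpoints are worded as improvement. An alternative of > 0, understood as improvement, is coherent for each scale, and a p-value against zero difference would register a benefit on either. What stands is that the same sentence serves two opposite scales and no order of subtraction is written.

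**Does the primary hypothesis contradict its sample size and its table?** That reading is tempting but too strong. An N of 15 exceeds the one-sided requirement and so satisfies it. The table row names only the null, which is the same under both readings, and the general 5% level states no sides. The 95% intervals in the SAP belong to responder rate, time to treatment failure and medication use; the primary table has no interval row. What stands is narrower: the figure given as required does not follow from the written one-sided test at the stated inputs, and it does follow from a two-sided one.

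**Is the effect small?** Yes, at the planned effect. The larger verdict differences need a true effect of half the plan or heavy dropout. The two secondary tests are also declared unadjusted for multiplicity.

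**Conclusion.** The point holds as a should-fix wording defect in operative analysis text.

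- The elbow variable in SAP 4.1.3.1 to 4.1.3.3 is wrong as written, although the intended variables are clear.
- The sign of change is undefined, and AOFAS and PGA improve in opposite directions under one shared rule.
- The primary test is written one-sided at an unqualified 5%, while the required N matches a two-sided 5% test at SD 2.5.

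The third item concerns the success rule, not power. It is the difference between a 5% and a 2.5% false-positive rate for claiming benefit, or 0.86 against 1.03 points at n = 25, SD 2.5. At the planned 2 points with n = 25, the verdict changes in 1.8% of trials or fewer.

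These figures assume normally distributed changes, the SD range in the documents and, unless stated otherwise, 25 evaluable subjects. That 15 came from a two-sided calculation is inferred from the match; the documents do not say so.

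**What to change.** In the SAP:

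1. Replace the elbow pain score with the named score in 4.1.3.1 (Lequesne), 4.1.3.2 (AOFAS) and 4.1.3.3 (PGA).
2. Define change so that positive means improvement: baseline minus visit for NRS and PGA, visit minus baseline for AOFAS. Give PGA percent change the same sign. The ankle documents do not show the Lequesne direction, so take it from the hip protocol.
3. State the sidedness once and use it in the hypothesis, the sample size and the table p-value. The preferred choice is two-sided 5%, with benefit claimed only if the mean change is positive; N = 15 then stands. If one-sided 5% is kept, restate the required N as 12 at SD 2.5 and label the p-value one-sided.

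**Cost.** No extra patients or data. Under the two-sided choice, power for 2 points at n = 25, SD 2.5 falls from 98.7% to 97.0%. The SAP text is shared, so the hip and shoulder analyses change too and must be checked against their protocols, which are not among the documents reviewed.

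Protocol 9.1 holds both the hypothesis and the figure of 15, so either choice calls for aligning it. Protocol 13.3 requires amendments to be signed and submitted to the authorities and ethics committees, so this can wait for the next amendment. Until then, any benefit claimed under the two-sided rule also meets the protocol's one-sided test at 5%.
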